4.2 Discussion of Study Design

Choice of Control Group

Ruxolitinib is the current standard treatment that is approved for patients with MF and induces improvement in splenomegaly and disease-related symptoms compared with placebo or best available therapy.² This study compares navitoclax in combination with ruxolitinib to placebo in combination with ruxolitinib. The choice of control group allows for a double-blind assessment of the contribution of navitoclax to the safety and efficacy of the backbone treatment of ruxolitinib.

Appropriateness of Measurements

Standard statistical, clinical, and laboratory procedures will be utilized in this study. All efficacy measurements in this study are standard for assessing disease activity in subjects with MF. All clinical and laboratory procedures in this study are standard and generally accepted.

Suitability of Subject Population

JAK2 inhibition induces down-regulation of the anti-apoptotic protein myeloid cell leukemia 1 (MCL-1) suggesting a role for navitoclax, a BCL-XL inhibitor, in the treatment of myeloproliferative neoplasms including MF. Therefore, subjects diagnosed with MF (PMF or SMF) represent the target population for this study.

Selection of Doses in the Study

The recommended starting dose of ruxolitinib for MF is according to the approved label and is based on the subject's baseline platelet count determined within 24 hours prior to the first dose: 20 mg twice daily ($> 200 \times 10^9/L$) or 15 mg twice daily ($100 \times 10^9/L$ to $200 \times 10^9/L$). The investigator may adjust the starting dose of ruxolitinib as medically appropriate after consultation with the AbbVie TA MD/SD, with subsequent increase in dose as shown in [Table 1](#).

As a BCL-X_L inhibitor, navitoclax causes thrombocytopenia via intravascular apoptosis of platelets. AbbVie internal data indicate that the effect of navitoclax on platelet reduction is exposure-related but may be diminished upon continued administration. Accordingly, thrombocytopenia may occur with navitoclax upon exposure to sufficient navitoclax concentrations. Additionally, thrombocytopenia and anemia are the primary reasons for ruxolitinib dose reductions.¹²

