Such an event can result from use of the drug as stipulated in the protocol or labeling, as well as from "special situations," such as accidental or intentional overdose, medication error, occupational or accidental exposure, off-label use, drug abuse, drug misuse, or drug withdrawal, all which must be reported whether associated with an adverse event or not. Any worsening of a pre-existing condition or illness is considered an adverse event. Worsening of disease under study or underlying cancer (serious or nonserious event) should be collected as an adverse event due to disease progression on the eCRF. Worsening in severity of a reported adverse event should be reported as a new adverse event. Laboratory abnormalities and changes in vital signs are considered to be adverse events only if they result in discontinuation from the study, necessitate therapeutic medical intervention, meets protocol specific criteria (see Section 6.2 regarding toxicity management), and/or if the investigator considers them to be adverse events.

The investigators will monitor each subject for clinical and laboratory evidence of adverse events on a routine basis throughout the study. All adverse events will be followed to a satisfactory conclusion.

An elective surgery/procedure scheduled to occur during a study will not be considered an adverse event if the surgery/procedure is being performed for a pre-existing condition and/or the surgery/procedure has been pre-planned prior to study entry. However, if the pre-existing condition deteriorates unexpectedly during the study (e.g., surgery performed earlier than planned), then the deterioration of the condition for which the elective surgery/procedure is being done will be considered an adverse event. Hospitalization for the purpose of monitoring platelet counts post study drug administration is not considered an adverse event or serious adverse event. If the hospitalization is prolonged due to an event not related to monitoring platelet counts, then adverse event/serious adverse event criteria is to be assessed.

If an adverse event, whether associated with study drug or not, meets any of the following criteria, it is to be reported to AbbVie clinical pharmacovigilance as a serious adverse event within 24 hours of the site being made aware of the serious adverse event (refer to Section 4.2 of the Operations Manual for reporting details and contact information):

Death of Subject	An event that results in the death of a subject.

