Life-Threatening	An event that, in the opinion of the investigator, would have resulted in immediate fatality if medical intervention had not been taken. This does not include an event that would have been fatal if it had occurred in a more severe form.
Hospitalization or Prolongation of Hospitalization	An event that results in an admission to the hospital for any length of time or prolongs the subject's hospital stay. This does not include an emergency room visit or admission to an outpatient facility.
Congenital Anomaly	An anomaly detected at or after birth, or any anomaly that results in fetal loss.
Persistent or Significant Disability/Incapacity	An event that results in a condition that substantially interferes with the activities of daily living of a study subject. Disability is not intended to include experiences of relatively minor medical significance such as headache, nausea, vomiting, diarrhea, influenza, and accidental trauma (e.g., sprained ankle).

Important Medical Event Requiring Medical or Surgical Intervention to Prevent Serious Outcome

An important medical event that may not be immediately life-threatening or result in death or hospitalization, but based on medical judgment may jeopardize the subject and may require medical or surgical intervention to prevent any of the outcomes listed above (i.e., death of subject, life threatening, hospitalization, prolongation of hospitalization, congenital anomaly, or persistent or significant disability/incapacity). Additionally, any elective or spontaneous abortion or stillbirth is considered an important medical event. Examples of such events include allergic bronchospasm requiring intensive treatment in an emergency room or at home, blood dyscrasias or convulsions that do not result in inpatient hospitalization, or the development of drug dependency or drug abuse.

All adverse events reported from the time of study drug administration until 30 days after the last dose/discontinuation of study drug administration will be collected, whether solicited or spontaneously reported by the subject. In addition, study procedure-related serious and nonserious adverse events will be collected from the time the subject signs the study-specific informed consent.

The following definitions will be used for serious adverse reactions (SARs) and suspected unexpected serious adverse reactions (SUSARs):

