Navitoclax accelerates apoptosis of circulating mature platelets whether endogenous or transfused. This mechanism of toxicity differs from the thrombocytopenia caused by ruxolitinib and other conventional chemotherapy (i.e., toxicity to platelet progenitors in the bone marrow) and should, therefore, be managed according to the guidelines provided in [Table 1](#), unless previously discussed and approved with the AbbVie TA MD/SD.

Hematology samples must be collected within 24 hours prior to the first dose of study drug to determine dose of study drug, at 4 hours after the first dose of study treatment, and on Day 2 (see Activity Schedule, [Appendix D](#), and Operations Manual, Section 3.14). The investigator should consider additional hematology labs on Day 3 and/or Day 4 for subjects with a lower baseline platelet count and for subjects who experience a > 40% decrease in platelet count on Day 2 from the pre-dose platelet count. Additional hematology labs may be performed based on platelet counts as medically indicated at the investigator's discretion.

Any Grade ≥ 2 bleeding event (regardless of platelet count) will require interruption of dosing. Upon resolution of a Grade ≥ 2 bleeding event, study drug treatment may be reintroduced at the same or lower dose level (in consultation with the AbbVie TA MD/SD), provided the patient is asymptomatic with no evidence of an active bleeding.

If platelet transfusions are required in response to active bleeding, navitoclax/placebo dosing should be interrupted. It should be noted that platelet response with transfusions may not follow typical platelet kinetics of thrombocytopenia as with typical chemotherapy-induced thrombocytopenia. Procedures consistent with local institutional blood banking guidelines regarding platelet transfusions should be followed.

Platelet Transfusion Recommendations:

If platelet transfusion is deemed necessary, the treating physician should be aware that due to the rapid apoptotic effect of navitoclax on mature platelets, the increase in platelet counts post-transfusion may be lower and the duration of response may be shorter. Therefore, donor platelets collected as recently as possible prior to transfusion should be used. Additional transfusions may be necessary to achieve the desired platelet count. Post-transfusion platelet count monitoring should include:

- A platelet count obtained 10 to 60 minutes post transfusion.

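### Protocol Section 6.1 exempts platelet-monitoring hospital stays without limiting the exemption to planned stays, so serious thrombocytopenia may be under-counted

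*Protocol*

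**What the plan says.** Two consecutive sentences in Protocol Section 6.1 govern these stays. The first is the exemption: "Hospitalization for the purpose of monitoring platelet counts post study drug administration is not considered an adverse event or serious adverse event". The second makes AE/SAE assessment necessary under one condition: "If the hospitalization is prolonged due to an event not related to monitoring platelet counts". Neither mentions planned, first-dose or protocol-required stays.

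The hospitalization criterion for an SAE, in the same section, reads: "An event that results in an admission to the hospital for any length of time or prolongs the subject's hospital stay". It is one of several criteria applied to an adverse event.

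Section 6.1 also says when a laboratory abnormality is an AE: if it leads to discontinuation from the study, or if it would "necessitate therapeutic medical intervention, meets protocol specific criteria (see Section 6.2 regarding toxicity management), and/or if the investigator considers them to be adverse events". Among its examples of important medical events it lists "blood dyscrasias or convulsions that do not result in inpatient hospitalization".

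On platelets, Section 6.2 requires hematology samples before the first dose, "at 4 hours after the first dose of study treatment, and on Day 2". Investigators are asked to consider further tests on Day 3 and/or Day 4 for subjects with a lower baseline count and for "subjects who experience a > 40% decrease in platelet count on Day 2 from the pre-dose platelet count". Neither Section 6.2 nor the Activity Schedule (Appendix D) describes a planned inpatient stay. Section 4.2 says that "navitoclax causes thrombocytopenia via intravascular apoptosis of platelets", and Section 2.2 names thrombocytopenia as the main toxicity limiting the navitoclax dose.

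**The concern.** An exemption for observation stays is reasonable if it covers a stay arranged in advance in which nothing happens. As worded, it turns on the purpose of the stay, and an admission after a sharp platelet fall can honestly be described as being for monitoring. If that stay is extended because counts remain low, the cause is platelet-related, so the second sentence does not clearly bring it back into assessment.

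The classification has consequences. SAEs go to the sponsor within 24 hours (Section 6.1) and are reviewed daily, while laboratory and AE data are reviewed weekly (Section 5.5). Seriousness also drives the serious row of the AE overview (SAP 9.2.2), the SAE tables and listings (SAP 9.2.4), and the serious row when that overview is repeated for the thrombocytopenia search (SAP 9.2.5 and Appendix B). The ambiguity falls on the toxicity for which a between-arm comparison of serious events matters most.

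**Working it through.** The plan gives no figure to reproduce here. The check is mainly textual, followed by a short illustration of scale.

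**Step 1: compare with the neighbouring exemption.** The same paragraph of Section 6.1 exempts elective procedures, but only for a pre-existing condition and/or where planned before study entry, and it restores AE status if that condition deteriorates unexpectedly. The platelet exemption has no planning limit, and its only route back excludes platelet monitoring.

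**Step 2: apply the text to a case.** Suppose no stay was planned. The count falls below 50 x 10^9/L on Day 2, the subject is admitted so that counts can be followed, and the stay is extended because they remain low.

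- Reading A: the purpose is monitoring, so the admission is exempt. The prolongation is platelet-related, so assessment is not reopened. The hospitalization criterion is not met.
- Reading B: the stay is not an event, but the platelet fall is. Table 1 calls for interruption at that count, so the fall can be an AE as meeting Section 6.2 criteria. If that AE resulted in the admission, it is serious.

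No sentence says which reading prevails, so two sites could classify the same case differently.

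**Step 3: separate what is exposed from what is not.**

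| Exposed (depends on seriousness) | Not exposed |
|---|---|
| Serious-TEAE row, SAP 9.2.2 | Grade rows, and rows for interruption, reduction and discontinuation, SAP 9.2.2 |
| SAE tables and listings, SAP 9.2.4 | TEAEs by preferred term and maximum grade, SAP 9.2.3 |
| Serious row of the thrombocytopenia overview, SAP 9.2.5 | Overall thrombocytopenia incidence and risk difference, SAP 9.2.5 |
| 24-hour reporting, Protocol 6.1 | Grade 3/4 laboratory shifts and platelet boxplots, SAP 9.3 |

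**Step 4: scale.** About 230 subjects randomized 1:1 (Protocol 4.1) gives 230 / 2 = 115 per arm, assuming all are treated. One reclassified subject moves an arm's incidence by 1 / 115 = 0.87 percentage points.

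Let p be the true rate of serious thrombocytopenia in an arm, and f the share whose only seriousness criterion is an exempted stay. The observed rate is p x (1 - f), and the number lost is 115 x p x f. The documents give neither p nor f, so every value of p and f below is an assumption, with f equal in both arms.

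| p, navitoclax vs control | f | Lost, navitoclax | Lost, control | Risk difference, true to observed (points) |
|---|---|---|---|---|
| 5% vs 2% | 50% | 2.9 | 1.2 | 3.0 to 1.5 |
| 10% vs 3% | 25% | 2.9 | 0.9 | 7.0 to 5.3 |
| 10% vs 3% | 50% | 5.8 | 1.7 | 7.0 to 3.5 |
| 10% vs 3% | 75% | 8.6 | 2.6 | 7.0 to 1.8 |
| 15% vs 5% | 50% | 8.6 | 2.9 | 10.0 to 5.0 |

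For example, at 10% and f = 50%, 115 x 0.10 x 0.50 = 5.75 subjects. At f = 0 nothing is lost. With equal f the risk ratio does not change (10/3 = 3.33 throughout the second scenario); only the absolute difference shrinks.

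**The case against.** The strongest reply is that the text exempts a stay and not the thrombocytopenia. The seriousness criteria apply to adverse events, so an observation stay without an event never met them, and the two rules can be read together. Monitoring is an activity, whereas a persistently low count is an event, so the second sentence can be taken to leave only extra observation time exempt. That reading is fair, and it defeats any claim that the protocol contradicts itself outright. It does not remove the difficulty, because nothing in the text makes a site adopt it.

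A second reply is that other routes to seriousness remain, including death, life-threatening events, disability and important medical events, and that admission for transfusion or to treat bleeding is not monitoring. This stands, and it limits how many events could be lost. The protection is partial: the life-threatening and important-medical-event criteria rest on investigator judgment, and the blood-dyscrasia example concerns cases without inpatient admission, so it does not squarely fit an admitted subject.

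Third, a reader might infer that the IDMC's picture of platelet toxicity is biased. The documents do not support that. The IDMC sees unblinded AEs and laboratory results (Section 5.12), so only its view of serious events is exposed.

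Finally, SAE reporting details are referred to Operations Manual Section 4.2, which was not in the text available for this review and might clarify the rule.

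**Conclusion.** The point holds as an ambiguity in a reporting definition that may cause serious thrombocytopenia to be under-counted. Only the hospitalization route to seriousness is weakened.

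A reader might go further and infer that the protocol expressly excludes unplanned admissions for severe platelet falls, and that serious events are therefore lost mainly from the navitoclax arm by several percentage points. The documents do not support that. Excluding such admissions is one of two open readings. Greater loss under navitoclax is an inference from its mechanism and from Study M16-109, where 83% of subjects had navitoclax doses reduced, mainly for thrombocytopenia (Section 4.2). Those subjects had already received ruxolitinib, and navitoclax was escalated to 300 mg. Against the inference, ruxolitinib lowers platelets in both arms of this trial and sites are blinded.

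The documents give no rate of platelet-related admission and no share that would be exempted, so the size is unknown and could be zero. The only figure that follows from the plan is about 0.87 points per reclassified subject, assuming 115 treated per arm. The change is worth making because it is cheap and concerns navitoclax's principal toxicity.

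**What to change.** In Section 6.1:

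1. Limit the exemption to observation stays scheduled before dosing in which no AE occurs.
2. Delete the qualifier about platelet monitoring from the second sentence, so that a stay prolonged by any event is assessed.
3. State that a platelet fall that causes an admission or prolongs a stay is assessed against the AE/SAE criteria of that section.

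Where exempted stays have been recorded, ask sites to re-assess them. The documents do not show whether such stays occurred or were captured, so this step may be partial.

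The change affects reporting only and leaves the management of subjects as it is. It costs a short protocol clarification, site queries where records exist, a few more expedited SAE reports and a slightly less favourable SAE table. The SAP tables need no change, since they take seriousness as reported.

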6.2 Toxicity Management

All subjects should be monitored according to the Activity Schedule in [Appendix D](#) for new-onset non-hematologic toxicity and renal toxicities, with dose delay or reduction as appropriate.

Navitoclax/Placebo

Navitoclax may be associated with cytopenias, notably thrombocytopenia, based on observations made of subjects during previous clinical trials in other indications and in the ongoing Study M16-109.

The guidelines noted below should be implemented for appropriate dosing and management of all subjects for safety. If additional dose reductions or modifications that are thought to be necessary by the investigator, a discussion with the AbbVie TA MD/SD is required.

- If a navitoclax/placebo interruption is necessary, navitoclax/placebo may be reintroduced at the same or lower dose based on the guidance below and in [Table 1](#).
 - Current dose level 200 mg once daily; reduce to 100 mg once daily, then 50 mg once daily
 - Current dose; 100 mg once daily; reduce to 50 mg once daily.
- The same navitoclax/placebo dose level shall not be attempted more than twice consecutively without prior approval from the AbbVie TA MD/SD.
- Intermediate dose levels of navitoclax/placebo (e.g., 150 mg once daily) may be administered for moderate dose adjustments.

Ruxolitinib

For ruxolitinib, in addition to the dose modification guidelines provided below and in [Table 1](#), the local, approved product label should be referenced for drug-drug interactions, precautions, monitoring, and dose adjustment guidelines for subjects with hepatic or renal impairment and all hematological and non-hematological toxicities.

For subjects who require interruption of ruxolitinib per the label but are considered to be at increased risk for exacerbation of splenomegaly and significant symptoms, ruxolitinib dose can be tapered by the Investigator in consultation with the AbbVie TA MD/SD followed by interruption.

Decisions regarding continued dosing, including the navitoclax/placebo or ruxolitinib dose level to be administered, for individual subjects will be medically managed by the investigator and consultation with the AbbVie TA MD/SD is recommended. Dosing interruptions greater than 28 days or additional dose modifications must be discussed with the AbbVie TA MD/SD.

Management of Thrombocytopenia and Bleeding Events

Navitoclax accelerates apoptosis of circulating mature platelets whether endogenous or transfused. This mechanism of toxicity differs from the thrombocytopenia caused by ruxolitinib and other conventional chemotherapy (i.e., toxicity to platelet progenitors in the bone marrow) and should, therefore, be managed according to the guidelines provided in [Table 1](#), unless previously discussed and approved with the AbbVie TA MD/SD.

Hematology samples must be collected within 24 hours prior to the first dose of study drug to determine dose of study drug, at 4 hours after the first dose of study treatment, and on Day 2 (see Activity Schedule, [Appendix D](#), and Operations Manual, Section 3.14). The investigator should consider additional hematology labs on Day 3 and/or Day 4 for subjects with a lower baseline platelet count and for subjects who experience a > 40% decrease in platelet count on Day 2 from the pre-dose platelet count. Additional hematology labs may be performed based on platelet counts as medically indicated at the investigator's discretion.

Any Grade ≥ 2 bleeding event (regardless of platelet count) will require interruption of dosing. Upon resolution of a Grade ≥ 2 bleeding event, study drug treatment may be reintroduced at the same or lower dose level (in consultation with the AbbVie TA MD/SD), provided the patient is asymptomatic with no evidence of an active bleeding.

If platelet transfusions are required in response to active bleeding, navitoclax/placebo dosing should be interrupted. It should be noted that platelet response with transfusions may not follow typical platelet kinetics of thrombocytopenia as with typical chemotherapy-induced thrombocytopenia. Procedures consistent with local institutional blood banking guidelines regarding platelet transfusions should be followed.

Platelet Transfusion Recommendations:

If platelet transfusion is deemed necessary, the treating physician should be aware that due to the rapid apoptotic effect of navitoclax on mature platelets, the increase in platelet counts post-transfusion may be lower and the duration of response may be shorter. Therefore, donor platelets collected as recently as possible prior to transfusion should be used. Additional transfusions may be necessary to achieve the desired platelet count. Post-transfusion platelet count monitoring should include:

- A platelet count obtained 10 to 60 minutes post transfusion.
- A platelet count obtained approximately 24 hours (± 1 hour) post transfusion.

Management of Neutropenia

There is a potential for clinically significant neutropenia given the toxicity profiles of both ruxolitinib and navitoclax. The management of neutropenia guidelines, as listed in [Table 1](#) and below, should be implemented for all subjects unless previously discussed and approved with the AbbVie TA MD/SD.

- For Grade 3 neutropenia in addition to interruption as listed in [Table 1](#), support with G-CSF and/or prophylaxis with antibiotics may be considered at the discretion of the investigator.
- For Grade 4 neutropenia in addition to interruption as listed in [Table 1](#), support with G-CSF and/or prophylaxis with antibiotics may be considered at the discretion of the Investigator. If, in the opinion of the investigator, ruxolitinib dose can be resumed prior to recovery of ANC $\geq 1.0 \times 10^9/L$ or needs a dose reduction, consultation with the AbbVie TA MD/SD is necessary.

At any time during the study, if the subject presents with febrile neutropenia, navitoclax/placebo and ruxolitinib, if applicable, should be interrupted until resolution of the fever or infection.

Table 1. Dose Adjustment Guidelines for Thrombocytopenia and Neutropenia

 • After navitoclax/placebo and/or ruxolitinib dose modification, platelet counts should be rechecked approximately 7 days or sooner as clinically applicable until at least 2 consecutive laboratory values indicate stable platelet count. • If treatment is interrupted for platelet count $< 50 \times 10^9/L$, recheck platelets approximately every 2 to 3 days until recovery of platelets to $\geq 50 \times 10^9/L$. • Navitoclax/Placebo Dose levels for daily dosing: 200 mg, 150 mg, 100 mg, 75 mg, or 50 mg. 		
Hematology Results	Navitoclax/Placebo	Ruxolitinib per approved local label
Dose Modification for Thrombocytopenia		
Platelet counts $\geq 125 \times 10^9/L$	
 • Maintain dose if current navitoclax/placebo dose is 200 mg QD. • Increase dose by one dose level if current navitoclax/placebo dose is ≤ 150 mg QD and has been administered for at least 7 days without any dose modification or interruption. 	
 • Increase dose to the label recommended dose for subjects who received lower starting dose of ruxolitinib than the label recommended dose if platelet counts are stable and current dose of ruxolitinib has been administered for at least 7 days without any dose modification or interruption.
Platelet counts $\geq 100 \times 10^9/L$ to $< 125 \times 10^9/L$	
 • Maintain dose if current navitoclax/placebo dose is ≥ 150 mg QD. • Increase dose by one dose level if current navitoclax/placebo dose is ≤ 100 mg QD and has been administered for at least 7 days without any dose modification or interruption. 	
 • Maintain current ruxolitinib dose if receiving ≤ 15 mg twice daily. • Reduce dose to one dose level lower twice daily if current ruxolitinib dose ≥ 20 mg twice daily.
Platelet counts $\geq 75 \times 10^9/L$ to $< 100 \times 10^9/L$	
 • Maintain dose if current navitoclax/placebo dose is ≥ 150 mg QD. • Increase dose by one dose level if current navitoclax/placebo dose is ≤ 100 mg QD and has been administered for at least 7 days without any dose modification or interruption. 	
 • Maintain current ruxolitinib dose if receiving ≤ 10 mg twice daily. • Reduce dose to 10 mg twice daily if current ruxolitinib dose ≥ 15 mg twice daily.

 • After navitoclax/placebo and/or ruxolitinib dose modification, platelet counts should be rechecked approximately 7 days or sooner as clinically applicable until at least 2 consecutive laboratory values indicate stable platelet count. • If treatment is interrupted for platelet count $< 50 \times 10^9/L$, recheck platelets approximately every 2 to 3 days until recovery of platelets to $\geq 50 \times 10^9/L$. • Navitoclax/Placebo Dose levels for daily dosing: 200 mg, 150 mg, 100 mg, 75 mg, or 50 mg. 		
Hematology Results	Navitoclax/Placebo	Ruxolitinib per approved local label
Platelet counts $\geq 50 \times 10^9/L$ to $< 75 \times 10^9/L$	
 • Reduce dose to one dose level lower. • Maintain dose if current navitoclax/placebo dose is 50 mg QD and counts are stable and no risk for bleeding per investigator discretion. • Interrupt dosing if current navitoclax/placebo dose is 50 mg QD and platelet counts are not stable and there is a risk for bleeding. 	
 • Reduce dose to 5 mg twice daily.
Platelet counts $< 50 \times 10^9/L$	
 • Interrupt dosing and resume at one dose level lower than prior to interruption once platelet counts recover to $\geq 50 \times 10^9/L$. 	
 • Interrupt per local label. May taper if high risk for exacerbation in discussion with TA MD/SD. • Resume at same or lower dose once platelet counts recover $\geq 50 \times 10^9/L$.
Dose Modification for Neutropenia		
Absolute neutrophil count (ANC) $< 1.0 \times 10^9/L$ to $0.5 \times 10^9/L$	
 • Interrupt dosing and monitor hematology labs at least weekly until ANC $\geq 1.0 \times 10^9/L$. • Resume at one dose level lower than prior to interruption once ANC recover $\geq 1.0 \times 10^9/L$. 	
 • Maintain current dose or interrupt per local label if at risk for infection per investigator discretion.
Absolute neutrophil count (ANC) $< 0.5 \times 10^9/L$	
 • Interrupt dosing and monitor hematology labs at least weekly or often as needed until ANC $\geq 1.0 \times 10^9/L$. • Resume at one dose level lower than prior to interruption once ANC recover $\geq 1.0 \times 10^9/L$. 	
 • Interrupt per local label. May taper if high risk for exacerbation in discussion with TA MD/SD. • Resume at same or lower dose.

Management of Infections

Subjects who develop clinically significant infections should have navitoclax/placebo and ruxolitinib interrupted and restart study drug treatment when signs or symptoms of infection have resolved.

If clinically indicated, anti-infective prophylaxis should be implemented at the investigator's discretion, including appropriate prophylaxis for viral, fungal, bacterial, or *Pneumocystis jiroveci* pneumonia infections with close monitoring as there is a potential for drug-drug interactions.

Management of Other Toxicities

For non-hematologic events, the investigator may interrupt and/or modify dosing of either of the study drugs, as clinically indicated. Consultation with AbbVie TA MD/SD prior to interruption or dose modification is recommended.

Grade ≥ 3 gastrointestinal toxicity of nausea, vomiting, and diarrhea when additional supportive care fails, increase in AST, ALT, and bilirubin (Grade determined from baseline value per CTCAE criteria) that might be attributed to navitoclax or ruxolitinib will require interruption and possible discontinuation of dosing if no improvement. Study drug treatment may be reintroduced at the same or lower dose level (in consultation with the AbbVie TA MD/SD) if the laboratory results or symptoms return to Grade ≤ 1 or to baseline at study entry.

